8.4.6 Adverse Events of Special Interest

The following are defined as AESI in this study, if the event takes place after the first intake of study intervention:

- Any condition triggering close liver observation according to Section 10.5.
 - Any increase in liver enzymes meeting the following criteria needs to be reported as an adverse event to the Sponsor within 24 hours of the investigator's awareness for expedited reporting to the health authorities:
 - o ALT and/or AST >8x ULN OR
 - \circ ALT and/or AST >3x ULN with total bilirubin >2x ULN
 - The investigator may consider whether the observed increase in liver values would qualify as SAE.
- Post-menopausal bleeding: Any participant experiencing unexplained postmenopausal bleeding after randomization should be referred to a gynecologist and undergo a transvaginal ultrasound with subsequent investigation and management according to the gynecologist's clinical judgment and usual practice.

8.4.7 Medical Device Deficiencies

Medical devices are being provided by or on behalf of the Sponsor for use in this study. To fulfill regulatory reporting obligations worldwide, the investigator is responsible for the detection and documentation of events meeting the definitions of device deficiency that occur during the study with such devices.

The definition of a medical device deficiency can be found in Section 10.6.3.

21 SEP 2023 Page: 46 of 73

Device deficiencies associated with a medical device AE/SAE (as defined in Section 10.6) will follow the processes outlined in Section 8.4 of the protocol and shall be documented and reported as a complaint to Bayer and eCOA vendor by the investigator.

Device deficiencies not associated with a medical device AE/SAE will be communicated directly to the eCOA vendor by the study site.

All device deficiencies have to be reported to the device manufacturer by the eCOA vendor according to their manual.

8.5 Pharmacokinetics

Blood samples for measurement of elinzanetant and its principal metabolites in plasma for PK are to be collected at the time points given in the SoA (Section 1.3). PK sample is collected before the second PSG night (together with the safety lab sample) in the PSG lab shortly before intake of the study medication to obtain trough levels. The date and time of the last study medication intake prior to the PK sampling as indicated in the SoA (Section 1.3) and the time of all blood samples are to be documented.

If, for any reason, PK samples are taken outside of the pre-specified time window, the exact time that the sample was taken must be recorded. These time deviations are not to be considered as important deviations.

If a participant discontinues study medication permanently, no blood sampling for PK is required. PK analyses are based on a population modeling approach. Blood samples are considered valid for the population PK analysis under the following conditions:

- The dose amount and time of intervention intake prior to the blood sample is known
- The time of the blood sample collection is known.

The samples are to be collected and processed as described in detail in the respective Sample Handling Sheets as a part of a separate Laboratory manual.

Plasma concentrations of elinzanetant are determined using a validated LC-MS/MS. Quality control and calibration samples are analyzed concurrently with study samples. The results of calibration samples, quality control samples, and study samples will be reported in the Bioanalytical Reports, which will be included in the Clinical Study Report for this study. A re-opening of the database may become necessary in order to include the results of the PK measurements. In addition, selected metabolites may be quantified in plasma using a validated analytical method and evaluated and reported as described for elinzanetant.

The bioanalyst will be unblinded for analysis of study samples. Placebo samples will not be analyzed.

Intervention concentration information that would unblind the study will not be reported to investigative sites or blinded personnel until the study has been unblinded.

Population pharmacokinetic analysis of elinzanetant

Based on the plasma concentrations, the variability in elinzanetant PK will be analyzed using population PK modeling. Optionally, a population PK/PD model could be used to describe the effect of elinzanetant exposure on efficacy and safety. This analysis might start prior to database lock (eg, at the moment that approximately 80% of the expected PK samples have been measured). The final population PK model that will be applied to describe the PK of elinzanetant in the study population may be linked to relevant endpoints or parameters

21 SEP 2023 Page: 47 of 73

obtained in this study to investigate the relationship between elinzanetant exposure and response.

Population or nonlinear mixed effects PK models describe the relationship between dose, time, and the elinzanetant plasma intervention concentration. A previously developed population PK model for elinzanetant based on Phase 1 and 2 data will be applied to all valid PK samples to evaluate the relationship between variability in PK and covariates, (ie, intrinsic [eg, bodyweight, race] and extrinsic factors [eg, concomitant medication]) that are of clinical relevance. If necessary, the population PK model will be adapted to adequately fit the data. Individual PK parameters of elinzanetant will be calculated.

A separate Modeling and Simulation (M&S) Analysis Plan, providing details of the model development and evaluation will be provided before the start of the population PK analysis. Evaluation of the data will be presented in a separate M&S Report.

Appropriate measures will be taken to maintain blinding of the study team (eg, data access will be restricted to specific people involved in the analysis and members of the study team will neither have access to the randomization list nor to individual data).

8.6 Pharmacodynamics

Pharmacodynamic parameters are not evaluated in this study.

8.7 Genetics

Genetics are not evaluated in this study.

8.8 Biomarkers

In this study biomarkers e.g. related to mode-of-action-related effects or safety and biomarkers deemed relevant to investigate pathomechanims of sleep disturbances associated with menopause may be investigated. These investigations may include e.g., diagnostic, safety, pharmacodynamic, monitoring, or potentially predictive biomarkers.

PK samples (Section 8.5), safety lab samples (Section 10.2 and Section 10.5) and sleep laboratory data (Section 8.2.1) might be used for biomarker studies. For timing see SoA (Section 1.3).

The results of biomarker investigations may be reported separately (e.g. in a biomarker evaluation report).

8.9 Immunogenicity Assessments

Not applicable.

8.10 Medical Resource Utilization and Health Economics

Medical resource utilization and health economics parameters are not evaluated in this study.

9. Statistical Considerations

The analysis and reporting will be done on all data from all participants at the time the study ends.

The SAP will be finalized prior to database lock and it will include a more technical and detailed description of the statistical analyses described in this section. This section is a

21 SEP 2023 Page: 48 of 73

summary of the planned statistical analyses of the most important endpoints including primary and key secondary endpoints.

9.1 Statistical Hypothesis

The primary objective for the study is to estimate the treatment effect of elinzanetant compared to placebo in the change from baseline in WASO at Week 4 as measured by PSG. No hypotheses are planned to be tested.

9.2 Analysis Sets

For the purposes of analysis, the following analysis sets are defined:

Participant Analysis Set	Description
Full analysis set	All participants randomly assigned to study treatment.
Safety analysis set	All participants randomly assigned to study treatment who were exposed to study treatment at least once.

The full analysis set is used to analyze endpoints related to the efficacy objectives and participants will be analyzed according to their randomized study treatment. The Safety Analysis Set is used to analyze the endpoints and assessments related to safety and participants will be analyzed according to the study treatment received.

9.3 Statistical Analyses

9.3.1 General Considerations

The statistical analyses will be performed in SAS and/or ValidR. The versions used will be specified in the SAP.

All variables will be summarized using descriptive statistics as appropriate by study treatment. Continuous variables will be summarized using at least the following descriptive statistics: number of non-missing observations, arithmetic mean, standard deviation, median, minimum and maximum. Categorical data will be summarized with frequency tables with the number of observations and percentages. Confidence intervals will be 2 sided with a confidence level of 90%.

Unless otherwise specified, baseline is defined as the latest available valid measurement at or before the start of study treatment. If the last observation available prior to randomization is the measurement from the screening visit, this would be used as the baseline value.

Important ICEs for this study are defined as:

- Temporary study treatment interruption, defined as:
 - a. Week 4 = Treatment taken <80% during weeks 1–4 OR treatment taken on <5/7 days during either Week 3 or 4.
 - b. Week 12 = Treatment taken < 80% during weeks 1-12 OR treatment taken on < 5/7 days during either Week 11 or 12.
- Permanent discontinuation of randomized study treatment
- Intake of prohibited concomitant medications having impact on efficacy

21 SEP 2023 Page: 49 of 73

The number of observed ICEs will be summarized by study treatment and overall for each intercurrent event.

9.3.2 Primary Endpoint/Estimand Analysis

9.3.2.1 Definition of Endpoint

The primary endpoint is the change from baseline in WASO at Week 4 as measured by PSG.

Polysomnography assessments will be performed on 2 consecutive nights during screening and at Week 4. The baseline WASO value will be the mean value of the 2 consecutive nights at screening. Similarly, the Week 4 value will be the mean value of the 2 consecutive nights at Week 4.

The change from baseline in WASO to Week 4 will be calculated as below:

Change from baseline = WASO mean value at Week 4 – WASO mean value at baseline

9.3.2.2 Main Analytical Approach

The primary endpoint will be analyzed using a MMRM on the change from baseline values at Week 4 and 12. Baseline value, study treatment, average weekly frequency of moderate-to-severe HFs (stratification factor) and week will be included as covariates in the model as well as the interaction terms baseline-by-week and study treatment-by-week. An unstructured covariance structure will be used. If convergence cannot be attained, alternative structures will be attempted. Additional details will be provided in the SAP. The least square means for each study treatment and the least square means differences comparing elinzanetant with placebo will be estimated with corresponding 90% confidence intervals.

Implementation of Strategies for Intercurrent Event Handling and Data Point Selection

Prior to performing the MMRM model, missing data will be handled in alignment with the estimand strategy for ICEs (described in Section 3).

The hypothetical strategy will be used to handle all of the ICEs in the primary estimand. This strategy will estimate the full efficacy potential of elinzanetant in the ideal situation if participants adhered to randomized study treatment up to Week 4 without taking prohibited concomitant medications impacting sleep. Data collected after the occurrence of any ICE will be discarded, and missing and unobserved data will be modeled using participants from the same study treatment who adhered to study treatment without taking prohibited concomitant medications impacting sleep to Week 4 and have observed data at Week 4.

Details of the imputation model will be provided in the SAP.

9.3.2.3 Sensitivity Analyses

A tipping point analysis will be applied to assess the sensitivity of the main analysis results to modeling of the missing data that occur in presence of all ICEs. This will be done by applying an unfavorable additive shift (referred to as delta adjustment) to the values imputed by the imputation model. Additional details on the tipping point analysis will be provided in the SAP.

9.3.2.4 Supplementary Analyses

A supplementary estimand for the primary endpoint will be estimated. The attributes are the same as the primary estimand (Section 3) except for the handling of the ICEs which will be addressed using the below strategies:

21 SEP 2023 Page: 50 of 73

ICEs	Proposed Strategy	Data Handling Method	Interpretation
Temporary study treatment interruption	Treatment Policy	Utilize the available data regardless of the occurrence of ICE	The treatment effect includes the effect of treatment interruptions
Premature discontinuation of study treatment	Hypothetical	Discard data collected after the ICE	The treatment effect that would be if participants who discontinue the randomized treatment remain untreated on randomized treatment
Intake of prohibited concomitant medication having impact on efficacy	Treatment Policy	Utilize the available data regardless of the occurrence of ICE	The treatment effect includes the effect of prohibited concomitant medications impacting sleep

ICE = Intercurrent event.

A treatment policy will be applied to handle the ICE temporary study treatment interruption and intake of prohibited concomitant medication having impact on efficacy. A treatment policy approach for these ICEs are appropriate as this likely reflects the behavior of the target population. According to this strategy, all collected data should be utilized in the analysis irrespective of occurrence of the ICEs. Although all participants are expected to be followed after these ICEs, some missing data may occur which will be handled in line with the estimand strategy.

A hypothetical strategy will be applied to handle the ICE premature discontinuation of study treatment to estimate the treatment effect that would be if participants who prematurely discontinue study treatment remain untreated (do not receive the experimental study treatment until the planned assessment timepoint). This approach reflects what would happen if participants remain in the study after premature discontinuation of study treatment. Missing and unobserved data will be modeled using placebo participants who remain on study treatment to Week 4 and have observed data at Week 4.

Full details of the analysis will be provided in the SAP.

9.3.3 Secondary Endpoints/Estimands Analysis

The secondary endpoints in this study are:

- Change from baseline in WASO at Week 12 as measured by PSG
- Change from baseline in sleep efficiency at Week 4 as measured by PSG
- Change from baseline in sleep efficiency at Week 12 as measured by PSG
- Change from baseline in PROMIS SD SF 8b total score at Week 4
- Change from baseline in PROMIS SD SF 8b total score at Week 12
- Change from baseline in ISI total score at Week 4
- Change from baseline in ISI total score at Week 12

The secondary endpoint change from baseline in WASO at Week 12 as measured by PSG will be derived similarly to the primary endpoint and analyzed using the same model as proposed for the primary efficacy analysis (see Section 9.3.2).

The secondary endpoints on sleep efficiency, PROMIS SD SF 8b and ISI will be analyzed descriptively by study treatment. In addition, the individual items in each patient-reported

21 SEP 2023 Page: 51 of 73

outcome will be summarized descriptively. All data will be utilized in the analysis regardless of the occurrence of ICEs. The calculation of the total scores for PROMIS SD SF 8b and ISI will be done according to the respective questionnaire guidelines.

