4.3 Secondary Endpoints Analysis

4.3.1 Secondary PSG Endpoints

- Change from baseline in WASO at week 12 as measured by PSG
- Change from baseline in sleep efficiency (SE) at week 4 as measured by PSG
- Change from baseline in SE at week 12 as measured by PSG

Version 2.0 Page: 25 of 57

The secondary PSG endpoints will be calculated analogous to the primary endpoint (Section 4.2.1). See Section 6.2.1 for more details on the definition for each parameter as measured by PSG.

4.3.1.1 Change from Baseline in WASO at Week 12

Change from baseline in WASO at week 12 will be analyzed in the same MMRM model as the primary endpoint for the main analysis and for the supplementary analyses (Section 4.2.2. and 4.2.3).

4.3.1.2 Change from Baseline in Sleep Efficiency (SE) at Week 4 and 12

For the analysis of change from baseline in SE at week 4 and week 12, the ICEs will be handled according to the treatment policy and no missing data imputation is planned. The actual values and change from baseline in SE will be summarized using descriptive statistics by study treatment and week using the FAS.

The change from baseline over time by study treatment will be shown using line plots for means and 95% CI. In addition, descriptive statistics for actual values and change from baseline in SE will be summarized by study treatment and individual nights (i.e., baseline night 1, baseline night 2, week 4 night 1, week 4 night 2, week 12 night 1, week 12 night 2).

The descriptive statistics for the actual and change from baseline in WASO by study treatment and week will also be summarized using the SLAS.

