89 - 95	Week 12

The absolute values and change from baseline values for PROMIS SD SF 8b total T-scores and total raw scores will be summarized using descriptive statistics by study treatment and week. The change from baseline over time by study treatment will be shown using line plots for means and 95% CI. In addition, the number and percentage of each response for each individual item will be summarized using frequency tables by study treatment and week. Stacked bar charts will also be produced showing the composition of responses for each item by treatment group and week.

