4.3.2.2 Insomnia Severity Index (ISI)

The ISI is a 7-item instrument that quantifies the participants perception of insomnia severity in the last 2 weeks (Bastien et al, 2001) and is collected during screening, at week 4 and at week 12/EoT. The items refer to: severity of sleep onset, sleep maintenance and early morning wakening problems, satisfaction with sleep pattern, noticeability of sleep problems by others, distress caused by the sleep difficulties and interference of sleep difficulties with daytime functioning. It is scored on a 5-point Likert scale from 0 to 4. The scores for each

Version 2.0 Page: 28 of 57

item are summed to produce the total score (maximum of 28) which allow categorization of severity of insomnia.

Total score severity categories:

- 0-7 = No clinically significant insomnia
- 8–14 = Subthreshold insomnia
- 15–21 = Clinical insomnia (moderate severity)
- 22–28 = Clinical insomnia (severe)

The baseline value will be the earliest assessment on day 1 or day 2. If both day 1 and day 2 assessment is not available, the baseline value will be the latest available assessment on or before day 4. Only assessments where ≥ 8 days of the 14-day recall period are outside of the impact duration of prohibited hormonal therapies and medication potentially confounding efficacy will be included. Details regarding the prohibited medications together with the impact duration are described in Section 6.3.

The absolute values and change from baseline values for ISI total score will be summarized using descriptive statistics by study treatment and week. The change from baseline over time by study treatment will be shown using line plots for means and 95% CI.

The ISI severity categories will be summarized using frequency tables by study treatment and week. Stacked bar charts showing the composition of severity categories at each week by treatment group will be produced.

In addition, the number and percentage of each response for each individual item will be summarized using frequency tables by study treatment and week. Stacked bar charts will also be produced showing the composition of responses for each item by treatment group and week.

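### Six of the seven secondary efficacy endpoints are analysed only descriptively, with no treatment difference adjusted for baseline and hot-flash stratum as there is for WASO

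*Protocol*

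**What the plan says.** Protocol 9.3.3 names WASO at Week 12, and sleep efficiency (SE), PROMIS SD SF 8b and ISI each at Weeks 4 and 12. WASO at Week 12 is modelled; SAP 4.3.1.1 confirms it: "Change from baseline in WASO at week 12 will be analyzed in the same MMRM model as the primary endpoint". For the rest, the protocol states: "The secondary endpoints on sleep efficiency, PROMIS SD SF 8b and ISI will be analyzed descriptively by study treatment".

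The SAP follows the protocol, measure by measure:

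- SE (SAP 4.3.1.2): "The actual values and change from baseline in SE will be summarized using descriptive statistics by study treatment and week using the FAS".
- PROMIS (SAP 4.3.2.1): "change from baseline values for PROMIS SD SF 8b total T-scores and total raw scores will be summarized using descriptive statistics".
- ISI (SAP 4.3.2.2): "The absolute values and change from baseline values for ISI total score will be summarized using descriptive statistics by study treatment and week".

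All three sections add line plots of arm means with 95% CIs. Intercurrent events (ICEs) are handled by treatment policy and nothing is imputed (SAP 4.3.1.2 and 4.3.2). SAP 4.8, which lists departures from the protocol analyses, adds no model for these measures.

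Two other places matter. SAP 4.2.2 specifies the WASO MMRM, with baseline, treatment, hot-flash (HF) stratum, week and treatment-by-week. SAP 4.1 says in general terms that differences between elinzanetant and placebo will be given. It does not say for which variables or by what method, and it sets CIs at 95% for descriptive statistics and 90% for the MMRM.

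**The concern.** SE sits under the primary objective and comes from the same PSG nights as WASO. PROMIS and ISI carry the secondary efficacy objective. Exploring efficacy on them calls for an estimate of the difference from placebo, and Protocol 4.2 itself expects a sizeable placebo response. A baseline is planned for each measure and randomisation is stratified by HF frequency, yet neither is used for these six endpoints.

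Two things are at stake. First, with about 35 to 39 women per arm, a raw difference in change is less precise than one adjusted for baseline. Second, a woman with a Week 4 value but no Week 12 value drops out of the Week 12 summary, whereas an MMRM would use her Week 4 value. SAP 6.4.1 says that women who stop treatment early also leave the study, so such gaps are to be expected.

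**Working it through.** **Count.** One secondary efficacy endpoint is modelled (WASO at Week 12) and 3 measures x 2 time points = 6 are descriptive, so 6 of 7. Protocol Table 3-1 also places TEAEs and laboratory abnormalities under a secondary safety objective; they are not counted here.

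**The plan's own figure.** Protocol 9.5 sizes the trial for WASO: SD 33.2 min, 35 per arm, and 90% probability that the 90% CI half-width is 14.7 min or less.

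- Expected half-width = t(0.95, 68) x 33.2 x sqrt(2/35) = 13.23 min.
- With 90% assurance, multiply by sqrt(chi2(0.90, 68)/68): 14.65 min.
- At 34 per arm the result is 14.89 min, so 35 is the smallest number that meets the target.

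The figure reproduces. It covers WASO only; no SD or baseline/follow-up correlation (rho) is given for SE, PROMIS or ISI. What follows is therefore in SD units, over assumed values of rho from 0.3 to 0.6.

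**Gain from adjustment, equal SDs.** Var(adjusted)/Var(change score) = (1 - rho^2)/(2 - 2 rho) = (1 + rho)/2.

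| rho | variance ratio | CI width ratio | CI narrower by | equivalent extra participants |
|---|---|---|---|---|
| 0.3 | 0.65 | 0.806 | 19% | 1/0.65 - 1 = 54% |
| 0.6 | 0.80 | 0.894 | 11% | 1/0.80 - 1 = 25% |

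At 35 per arm, the expected 90% half-width is 0.399 SD of change unadjusted. Adjusted, it is 0.322 SD at rho 0.3 and 0.357 SD at rho 0.6.

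**Gain from adjustment, unequal SDs.** Let k = baseline SD / follow-up SD. The variance ratio becomes (1 - rho^2)/(1 + k^2 - 2 rho k).

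- k = 0.7, rho 0.3: 0.91/1.07 = 0.850, width ratio 0.922, about 8% narrower.
- k = 0.7, rho 0.6: 0.64/0.65 = 0.985, width ratio 0.992, about 1% narrower.
- k = 1.3, rho 0.3: 0.91/1.91 = 0.476, width ratio 0.690, about 31% narrower.
- k = 1.3, rho 0.6: 0.64/1.13 = 0.566, width ratio 0.753, about 25% narrower.

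**Chance baseline imbalance.** At 39 per arm the between-arm baseline difference has SD sqrt(2/39) = 0.226 baseline SD. A change score already subtracts baseline, so with equal SDs only (1 - rho) of it carries through: 0.7 x 0.226 = 0.16 SD at rho 0.3, and 0.4 x 0.226 = 0.09 SD at rho 0.6. This is the same loss as in the table, not an additional one: (2 - 2 rho) - (1 - rho^2) = (1 - rho)^2.

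**The case against.** The strongest reply is that the choice is deliberate and fits the design. This is a pilot with objectives to explore, no hypotheses and no multiplicity scheme, sized for WASO at Week 4 alone. Protocol and SAP agree, and no decision in the documents depends on an adjusted SE, PROMIS or ISI estimate. That stands: the plan is neither contradictory nor miscalculated here. It does not argue against an adjusted estimate, because an estimation study is where a difference with its interval is the natural output, and the addition brings no test.

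A reader might infer that no between-arm contrast at all is planned for these endpoints. The documents do not support that. The sentence in SAP 4.1 can be read as promising a raw difference, and the table specifications are in a separate document. But the endpoint sections do not ask for a difference, and a raw one would be unadjusted and, by the SAP 4.1 rule, carry a 95% interval against 90% for WASO.

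A reader might also infer that the full 0.23 SD of chance imbalance enters the change score, or that a gain of 11-19% is assured. Neither holds: only 0.09 to 0.16 SD carries through under equal SDs, and the gain shrinks to 1-8% at k = 0.7.

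Last, the WASO model cannot simply be copied. SAP 4.2.2.1 ties it to discarding data affected by ICEs, while these endpoints use treatment policy. A likelihood model also treats women who withdrew as resembling those who stayed in their arm, given their observed data. That is not strictly treatment policy. The objection is right that this must be stated, though an observed-case summary used as an arm comparison rests on a stronger assumption. PRO baselines can also be missing under the prohibited-medication rule in SAP 4.3.2.1 and 4.3.2.2.

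**Conclusion.** The point holds as a missed analysis of modest size. For six of seven secondary efficacy endpoints, no treatment difference adjusted for baseline and HF stratum is specified, while WASO has one. An unadjusted difference may be intended under SAP 4.1, but that is unclear.

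The precision forgone is about 11-19% of CI width for rho 0.3 to 0.6 with equal baseline and follow-up SDs, and about 1-8% if the baseline SD is 0.7 of the follow-up SD. It is larger if the baseline is the more variable of the two. All of these rest on assumed correlations and SD ratios. The lack of adjustment does not bias the comparison over repeated randomisations, and neither the primary analysis nor the sample size is touched.

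**What to change.** In SAP 4.3.1.2, 4.3.2.1 and 4.3.2.2, keep the descriptive tables and add the following before unblinding:

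- An MMRM for change at Weeks 4 and 12 in each measure, with baseline value, treatment, week, actual HF stratum and treatment-by-week.
- All observed data used regardless of ICEs, in line with the treatment-policy handling already stated.
- A statement that values missing after study withdrawal are handled as missing at random.
- Least squares mean differences with 90% CIs at both weeks, as estimation only and without tests.

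The cost is a few SAP lines, three more model runs and one stated missing-data assumption; no new data are needed. Women without a valid baseline drop out of the model, as they already do from the change-score summaries. PROMIS weeks would follow the mapping in SAP Table 4-5, as in the descriptive tables.
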